15.0. Secondary Effectiveness Analyses (Secondary Outcomes)

Secondary Outcomes (Aim1a) Primary Statistical Hypotheses: Those in both active intervention conditions will show greater improvements in overall pain severity, pain intensity (MCID and overall), pain-related interference (MCID and overall) and related quality of life outcomes (social role functioning, physical functioning, and patient global impression of change) relative to those receiving usual care at the 3-month follow-up.

Secondary Outcomes (Aim1a) Secondary Statistical Hypotheses: Those in both active intervention conditions will show greater improvements in overall pain severity, pain intensity (MCID and overall), pain-related interference (MCID and overall) and related quality of life outcomes (social role functioning, physical functioning, and patient global impression of change) relative to those receiving usual care at the 6- and 12-months follow-ups (secondary time points).

Secondary Outcomes (Aim 1a) Analyses: Aim 1a will examine the impact of the active interventions on secondary outcomes. Analyses of these outcomes will follow the same proposed approach as Aim 1. We will use linear regression for continuous outcomes and Poisson regression for binary and count outcomes. We will use GEE^{21,22} to estimate regression models for longitudinal data using an independence working correlation matrix. We will calculate all standard errors using the robust sandwich estimator^{21,22} to account for within-person and within-health coach correlation or any misspecified variance structures. We will include an interaction between intervention arms and time indicators, and the primary time point for all secondary analyses will be 3 months following randomization and will include as covariates baseline levels of pain severity and all stratification variables.

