15.6 Secondary Effectiveness Analyses

Secondary Outcomes (Aim1a) Primary Statistical Hypotheses: Those in both active intervention conditions will show greater improvements in overall pain severity, pain intensity (MCID and overall), pain-related interference (MCID and overall) and related quality of life outcomes (social role functioning, physical functioning, and patient global impression of change) relative to those receiving usual care at the 3-month follow-up.

Secondary Outcomes (Aim1a) Secondary Statistical Hypotheses: Those in both active intervention conditions will show greater improvements in overall pain severity, pain intensity (MCID and overall), pain-related interference (MCID and overall) and related quality of life outcomes (social role functioning, physical functioning, and patient global impression of change) relative to those receiving usual care at the 6- and 12-months follow-ups (secondary time points).

Analyses of secondary outcomes (Aim 1a) will follow the same proposed approach as Aim 1. Linear regression will be used to assess continuous outcomes and Poisson regression for binary and count outcomes. An interaction between intervention arms and time indicators will be included, and the primary time point for all secondary analyses will be 3 months following randomization; baseline levels of pain severity and all stratification variables will be included as covariates.

The RESOLVE Statistical Analysis Plan (SAP) provides details on these planned secondary outcome analyses.

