03/29/22	Removed references to painTRAINER as an "application" and replaced with "online program" as it is not an application ("App") that can be downloaded to a mobile device but can only be used online via a web browser. Also removed "web-based" as descriptor and replaced with "online" as it is clearer to describe as "online CBT-based." (vs. web-based, CBT-based)	"Application" was inaccurate description.
03/29/22	Added information on sensitivity analysis related to population randomized after implementation of "enhanced" painTRAINER onboarding guidelines. [Section 14, page 20]	Requested by DSMB.
07/17/24	Corrected [name] institution on the title page which changed from KP CHR to KPWHRI. This was addressed in the modification of the Protocol to version	[name] transferred KP institutions (as of Jan. 1, 2023).

	5.0 (Nov. 2022). The protocol version info on the title page has also been updated to reflect this.	
07/17/24	Two corrections were made to the descriptions of outcomes in sections 3.2 and 3.3 to reflect the final protocol. This is not a change to the actual outcomes assessed, it is only a change to this SAP document which had 2 errors related to outcomes' descriptions. Specifically, in section 3.2, the description of the Guy/Farrar Patient Global Impression of Change stated "(1 item)", however as the Protocol accurately states, it should say "(1 item each for pain status and overall status)," i.e., 2 items. This has been corrected. In section 3.3, the exploratory outcomes related to "Examining the impact of the active interventions on high impact chronic pain and graded chronic pain" had been erroneously omitted from this document, although they are clearly stated in the study aims. This has also been corrected.	Error in descriptions.
07/17/24	Added inverse probability of missing weights (IPW) to address missing data for those missing all time points. Current missing data approach imputes data using pattern mixture approach only among those with at least one follow-up time point. Adding IPW allows for estimates to be interpreted among all randomized and not only among those with at least one follow-up time point.	Due to observed higher than expected rates of missing all outcomes across all time points (12.1%) this improvement in handling missing data was proposed by the masked Biostatistician, [name], who does not have access to the outcome data nor has seen any summary of data by treatment arm at the time of this modification.

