All data collection procedures and statistical analyses in this SAP will be finalized and approved by the RESOLVE Study Principal Investigator (PI) and Study Lead Statistician prior to the unblinding of the data. In addition, the data collection procedures and statistical analyses detailed in this SAP may be modified and are given precedence over the analytical plans outlined in the Study Protocol; however, any modifications or changes in the primary endpoint and/or its analysis will also be reflected in a protocol amendment. Any updates to the SAP will be thoroughly detailed and documented at the beginning of this document.

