11.0. Missing Data

The clinical investigation team will make substantial efforts to ensure complete collection of data for all patients, and to ensure minimal loss to follow-up to optimize evaluation of the primary effectiveness outcome. For the primary analyses, we will analyze those patients who have follow-up data. Any missing data will be assumed to be missing at random (MAR) given the adjustment of baseline covariates. However, in the event that a patient is lost to follow-up, the underlying reason(s) for dropping out will be tracked in order to help assess the mechanisms of missingness. We will analyze missing data and conduct sensitivity analyses as required (i.e., >15% missing outcome follow-up at 3 months or differential missingness by group). Specifically, we will address missing data in two ways. Our first approach will apply a pattern mixture imputation missing data approach that relaxes the MAR assumption conditioning on the patterns of missing data over time among those with at least one follow-up time measure and inverse probability weights (IPW) for those missing all follow-up time points.¹⁹ The second approach will be used as a sensitivity analysis assuming a worst-case, best-case approach. Specifically, for those with missing outcome data in the intervention arms we will assume they did not achieve the MCID in pain severity at each missing time point (worst-case). For those randomized to the usual care we will assume all achieved the MCID in pain severity at each missing time point (best-case). This sensitivity analysis will provide the extreme case in how small the intervention effect could be relative to usual care due to missing outcome data.

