14.0. Primary Effectiveness Analyses

Primary Outcome Statistical Hypothesis: Both active interventions (painTRAINER and virtual coach-led CBT-CP) are expected to result in a higher proportion of patients achieving MCID (30% reduction in overall BPI-SF score) in pain severity relative to those receiving usual care at 3-month follow-up (primary time point).

Secondary Time Point Statistical Hypotheses: Both active interventions (painTRAINER and virtual coach-led CBT-CP) are expected to result in a higher proportion of patients achieving MCID (30% reduction in overall BPI-SF score) in pain severity relative to those receiving usual care at the 6 and 12-month follow-ups (secondary time points).

Primary Outcome and Secondary Time Point Analyses: We will use modified Poisson regression^{20,21} fit using generalized estimating equations (GEE) to model the binary primary outcome, MCID in pain severity (30% reduction from baseline), 3 months (primary time point) and 6 and 12 months (secondary time points). We are employing modified Poisson (i.e., Poisson family with log link, but use robust standard errors to correct for mis-specified outcome variance) instead of logistic regression since the binary outcome is not rare and the estimate of interest is the relative risk. We will use a working independence correlation matrix and will calculate standard errors using the robust sandwich estimator to account for within-person and within-health coach correlation^{21,22} and account for the mis-specified mean-variance structure when using Poisson regression for a binary outcome.^{20,23} We will include interactions between each intervention and indicators of time (3, 6, 12 months) to estimate time-specific intervention effects; the primary comparisons will be between the interventions and usual care at 3 months (i.e., primary effectiveness will test the size of the intervention coefficient at the 3-months timepoint). We will adjust for baseline levels of pain severity, other stratification variables (sex, clinical site, and rural/medically underserved residency), and a priori variables predictive of outcome (multisite pain and co-occurring mental health condition). Specifically, we will fit the following mean model where Usual Care and 3 months are the reference groups:

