17.0. Exploratory (Tertiary) Effectiveness Analyses

We will examine the impact of the active interventions on exploratory outcomes using the same proposed approach for secondary outcomes outlined above in Section 15.0.

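### SAP 15.0 and 17.0 do not list the outcome's own baseline as a covariate for six secondary and exploratory outcomes; the main cost is precision, and adding it is cheap

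*SAP*

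**What the plan says.** SAP 15.0 opens with a general reference: "Analyses of these outcomes will follow the same proposed approach as Aim 1". It then gives an explicit covariate list: the models "will include as covariates baseline levels of pain severity and all stratification variables". Protocol 15.6 gives the same list: "baseline levels of pain severity and all stratification variables will be included as covariates". SAP 17.0 analyses the exploratory outcomes "using the same proposed approach for secondary outcomes outlined above in Section 15.0", and Protocol 15.9 does likewise.

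The outcome tables in SAP 3.2 and 3.3 show a baseline measurement for:
- two secondary outcomes: social role functioning and physical functioning;
- four exploratory outcomes: PHQ-8, GAD-7, sleep disturbance and long-term opioid use.

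The Aim 1 model in SAP 14.0 has response rows at 3, 6 and 12 months only, so a baseline score does not enter as a response either. SAP 13.0 mentions a baseline function or symptom score, but only when defining variables for descriptive tables.

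On missing data, SAP 11.0 states: "Any missing data will be assumed to be missing at random (MAR) given the adjustment of baseline covariates". The SAP change log entry of 07/17/24 records that 12.1% were missing all outcomes at every time point.

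**The concern.** A programmer following the written list would adjust PHQ-8 at 3 months for baseline BPI-SF pain severity and not for baseline PHQ-8. The own baseline is usually the strongest available predictor of a follow-up score. Leaving it out makes confidence intervals wider than the collected data require.

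Two further matters follow.
- SAP 15.0 does not say whether the dependent variable for continuous outcomes is the follow-up value or the change from baseline, although the mediator model in SAP 16.0 does specify change. Without the own baseline in the model, the two choices give different estimates and standard errors.
- The missing-at-random assumption is conditional on the adjusted covariates, so the covariate list helps to define it. Including the own baseline makes that assumption more plausible.

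**Working it through.** **The plan's own figure.** The documents give no sample size, SD or precision target for these six outcomes. The only stated figure is for the primary outcome: 621 evaluable per arm for 15% against 22.5% at 90% power. Simulating the SAP's two-step rule (omnibus test at 0.05, then pairwise test at 0.05) gives 90.8% power at 621 per arm with the third arm at 15%, and 91.2% with it at 22.5%. Then 621 / 0.80 = 776.25, rounded up to 777, and 3 × 777 = 2,331. None of this changes here; 621 per arm is used below only as the evaluable number.

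**Assumed inputs** (none are in the documents), for the five continuous outcomes, with equal SD at baseline and follow-up:
- r, own baseline with follow-up: 0.4 to 0.8, middle 0.6
- p, baseline pain severity with follow-up: 0.2 to 0.4, middle 0.3
- c, baseline pain severity with own baseline: 0.3 to 0.6, middle 0.45

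**Residual variance, in units of the outcome variance:**
- Listed covariates, follow-up value analysed: v1 = 1 − p² = 1 − 0.09 = 0.910
- Listed covariates, change analysed: v2 = 2(1 − r) − (p − c)² = 0.80 − 0.0225 = 0.778
- Own baseline added, either reading: v3 = 1 − (r² + p² − 2rpc)/(1 − c²) = 1 − 0.288/0.7975 = 0.639

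**Reduction, middle case:** 1 − 0.639/0.910 = 30% (value); 1 − 0.639/0.778 = 18% (change).

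**95% CI half-width for one pairwise comparison**, 1.96 × √(2v/621), before any coach clustering: 0.106 SD (value), 0.098 SD (change), 0.089 SD (own baseline added). The equivalent number per arm is 621 × 0.910/0.639 ≈ 885 (value) or 621 × 0.778/0.639 ≈ 756 (change).

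**Range.** I keep only combinations with p ≥ rc, where higher baseline pain does not predict a better outcome once the own baseline is known.

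| Reading | End | r, p, c | Variances | Reduction |
|---|---|---|---|---|
| Value | low | 0.4, 0.4, 0.6 | 0.840 to 0.800 | 5% |
| Value | high | 0.8, 0.24, 0.3 | 0.942 to 0.360 | 62% |
| Change | low | 0.8, 0.4, 0.5 | 0.390 to 0.360 | 8% |
| Change | high | 0.4, 0.4, 0.3 | 1.190 to 0.754 | 37% |

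Without that restriction the ends are 5% to 75% (value) and 0% to 37% (change). The 75% and 0% ends need a negative partial correlation of baseline pain with follow-up, as 37% of the unrestricted grid does, so I do not rely on them.

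**If the Aim 1 mental-health covariate carries over.** Suppose it correlates m = 0.3 to 0.5 with baseline PHQ-8 or GAD-7, 0.6m to 0.8m with follow-up, and 0.05 to 0.2 with baseline pain. The middle-case reduction for those two outcomes is then 18% to 29% (value) or 14% to 19% (change).

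**Bias.** In 2,000 simulated trials at the middle case, with complete data and no true effect, the mean estimate was within 0.001 SD of zero in every model. With about 12% missing all follow-ups and the same dependence of dropout on the own baseline in all arms, bias was at most 0.002 SD. Bias appeared only when dropout rose with the own baseline in one intervention arm alone. At odds ratios of 1.25 to 2.0 per SD it was −0.012 to −0.039 SD (value) or +0.009 to +0.029 SD (change), and at most 0.001 SD in size once the own baseline was included. These runs did not include the planned imputation or weighting.

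**Opioid baseline window.** Protocol 3.4 sets the survey date as Day 0 and places it in the baseline window (Day −89 to Day 0). SAP 3.3 sets the survey date as Day 1, with baseline ending at Day −1, so the survey day falls in the 3-month window.

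**The case against.** - **The reference to Aim 1 may already cover it.** In Aim 1, baseline pain severity is the outcome's own baseline, so following the same approach could mean adjusting each outcome for its own baseline. That reading is possible, and it is why the claim is that the covariate is not listed, not that it will certainly be left out. But both documents name pain severity in the explicit list, so at the least a clarification is needed.
- **This is an efficiency preference.** Four of the six outcomes are exploratory, no precision target is stated for any of them, and the middle-case gain is 0.009 to 0.017 SD in half-width. All true. It limits the weight of the point, but the change costs almost nothing and gives a better model than the one listed.
- **The size rests on assumed correlations.** It does. The SAP's wording about improvement leans towards change, for which the gain is the smaller of the two.
- **A reader might infer biased comparisons or inflated type I error.** The documents do not support that. They do not show arm-dependent dropout, and SAP 11.0 plans pattern-mixture imputation and inverse probability weights. I give no type I error figure: the simulated rates were for ungated pairwise tests, whereas SAP 10.0 applies an omnibus test first, and the simulation left out the planned imputation and weighting. Which variables enter the weights is a separate question for SAP 11.0.

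**Conclusion.** The gap is real and modest. For two secondary and four exploratory outcomes with a collected baseline, the written covariate list omits that baseline. That the covariate is unlisted is certain; the size of the gain is not. Under the stated assumptions the residual variance of the five continuous outcomes falls by 18% (change) or 30% (value) in the middle case, with plausible ranges of about 8% to 37% and 5% to 62%. No figure is claimed for binary opioid use.

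The comparisons remain valid with complete data or with dropout that does not depend on the own baseline differently by arm. A firmer missing-at-random assumption is a secondary benefit.

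The point does not extend to every outcome. Continuous pain severity already has its own baseline in the model. PGIC has no baseline. High-impact chronic pain is an entry criterion, so its baseline hardly varies; graded chronic pain is affected only if the baseline grade varies. Pain intensity and interference are components of the adjusted score, so their own subscale baselines add little.

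**What to change.** Before unblinding, amend SAP 15.0, with 17.0 inheriting the change:
1. Add a sentence such as: *each model also includes the baseline value of the outcome analysed, where one exists and varies*. Keep the existing covariates.
2. State whether the dependent variable for continuous outcomes is the follow-up value or the change. In the linear models the treatment estimate and its standard error are the same either way once the own baseline is included.
3. Exempt PGIC and high-impact chronic pain. Subscale baselines for intensity and interference are optional.
4. Reconcile the opioid baseline window between Protocol 3.4 and SAP 3.3 before using baseline opioid use as a covariate.
5. Give a rule for an occasional missing baseline score, such as single imputation, so that no randomized participant is dropped.

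Matching edits to Protocol 15.6 and 15.9 would be for consistency only, because SAP 2.0 says the SAP's analyses "are given precedence over the analytical plans outlined in the Study Protocol". The cost is a few SAP sentences, one reconciled window and one extra parameter per model. No new data are needed, because randomization follows baseline data collection.

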8.0. Randomization

After completion of the baseline data collection, study participants will be individually randomized in equal ratio to one of the three study arms.

Randomization will be stratified on:

Variable	Source
Sex	Sex from electronic health record (Male vs. Female or Other)
Pain severity score	Score on BPI-SF from baseline survey (< 7 vs. ≥ 7)
Clinical site	KPWA, KPNW, KPGA, Essentia
Rural/medically underserved residency	Residency geocode for Census Tract from electronic health record

Within each stratum, to contain concealment and balance randomization over time, a random permuted block design will be used with random variable block sizes of 3, 6, or 9 to ensure approximately equal accrual into the three study arms.

The TIN JHU/Tufts Lead biostatistician will develop the randomization scheme and the TIN Utah DCC will implement the scheme using the appropriate statistical software. The scheme to be implemented will be integrated into the study centralized tracking system.

Randomization will be conducted by KPWHRI research staff within the study centralized tracking system after consent and baseline assessment completion.

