13.0. Demographic and Baseline Characteristics

Demographics will include age, sex, race, and ethnicity and will be summarized by treatment group using descriptive statistics for each of the defined samples and for the effectiveness analyses. Baseline variables are defined as pre-randomization variables such as baseline function or symptom score, comorbidities or any other variables thought to be associated with primary or secondary outcomes, moderate intervention (subgroups) or predict drop-out. Candidate variables will include but are not limited to age, sex, race, ethnicity, rural/medically underserved residency, multiple pain conditions, mental health mood disorders, and negative social determinants of health (SDOH).

Descriptive statistics for all follow-up data will be provided by intervention arm. These descriptive statistics will include the mean, median, SD, maximum and minimum for continuous variables, and frequencies, percentage, and tabulations for categorical variables. Summary statistics will be performed on patient demographics, including age, sex, race, ethnicity, and other clinical characteristics, including medical history, and prior and concomitant interventions.

Subgroups defined by cut points are: 1) sex (male), 2) age (≥ 65 years), 3) race/ethnicity (White/Non-Hispanic, Black or African American/Non-Hispanic, Hispanic, Other), 4) rural/medically underserved residency, 5) multiple pain conditions (>1 pain condition based on ICD dx), 6) mood disorders (anxiety or depression based on ICD dx), and 7) negative/poor SDOH. Additional analysis of groupings of these factors will be dictated by group size and balance between groups.

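### The covariate list for secondary and exploratory models omits multisite pain and mental health condition, which the primary model includes: a small loss of precision and a narrower MAR assumption, cheaply removed

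*SAP*

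**What the plan says.** SAP 14.0 adjusts the primary model for baseline pain severity, the other stratification variables (sex, clinical site, rural/medically underserved residency) and "a priori variables predictive of outcome (multisite pain and co-occurring mental health condition"). Protocol 15.5 has the same set.

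SAP 15.0 opens its analysis paragraph with "Analyses of these outcomes will follow the same proposed approach as Aim 1". It closes by saying that the models "will include as covariates baseline levels of pain severity and all stratification variables". Protocol 15.6 agrees: "baseline levels of pain severity and all stratification variables will be included as covariates". SAP 17.0 analyses the exploratory outcomes "using the same proposed approach for secondary outcomes outlined above in Section 15.0", and Protocol 15.9 does likewise.

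SAP 8.0 stratifies randomization on sex, baseline BPI-SF score (below 7 against 7 or more), site and residency. Neither multisite pain nor mental health condition is a stratum, so neither enters the secondary models by that route.

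On missing data, SAP 11.0 states: "Any missing data will be assumed to be missing at random (MAR) given the adjustment of baseline covariates".

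**The concern.** The plan names two variables in advance as predictive, uses them for the primary outcome, and leaves them off the explicit list for most other outcomes without giving a reason. Two things are at stake.

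- **Precision.** A baseline variable that predicts the outcome reduces residual variance when it is in the model. Leaving it out gives up that gain.
- **Missing data.** SAP 11.0 defines its MAR assumption by the covariates adjusted for, so a shorter list is a stronger assumption. Planned retention is 80% (SAP 5.0), and the SAP change log records 12.1% missing every follow-up.

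There is also a drafting problem. The reference to Aim 1 and the list at the end of the same paragraph point to different covariate sets, so an analyst could fit either and claim to follow the plan.

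**Working it through.** **1. The lists side by side.**

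| Covariate | SAP 14.0 / Protocol 15.5 | SAP 15.0 / Protocol 15.6 (and SAP 17.0) |
|---|---|---|
| Baseline pain severity | yes | yes |
| Sex, site, rural/medically underserved residency | yes | yes (strata) |
| Multisite pain | yes | not listed |
| Co-occurring mental health condition | yes | not listed |

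MCID in pain severity at 6 and 12 months is a secondary outcome in SAP 3.2, but the arm-by-time terms of the SAP 14.0 model estimate it, with both variables included. The point does not apply there.

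**2. The plan's own sample size.** SAP 5.0 gives 621 evaluable per arm (1,863) for 15% against 22.5% at 90% power under Fisher's LSD. Simulating an omnibus Wald test and then pairwise Wald tests, each at 0.05, gives pairwise power at 621 per arm of 90.8% if the third arm equals usual care and 91.2% if it equals the effective arm. (It is 86.7% if the third arm lies midway.) For retention, 621/0.8 = 776.25, rounded up to 777, and 3 × 777 = 2,331. No covariates enter this calculation, so the point does not touch it. The documents give no precision figure for the secondary models.

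**3. Continuous outcomes.** Let r be the partial R² of the two variables given the short list. It is assumed, because the documents give no value. The short-list standard error is larger by the factor 1/√(1−r). The patients needed to offset this are 1,863 × r/(1−r).

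| r (assumed) | SE larger by | Patients of 1,863 | Power, if 90% with the full list |
|---|---|---|---|
| 1% | 0.5% | 19 | 89.7% |
| 3% | 1.5% | 58 | 89.1% |
| 5% | 2.6% | 98 | 88.5% |

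**4. Binary outcomes.** Modified Poisson models with robust standard errors were simulated at 621 per arm, 15% against 22.5%. Two binary covariates were assumed, each with 50% prevalence and the same risk ratio (RR). The patient equivalent is 1,863 × [(SE ratio)² − 1].

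| Covariate RR (assumed) | SE larger by | Patients of 1,863 |
|---|---|---|
| 0.9 | 0.06% | 2 |
| 0.75 | 0.45% | 17 |
| 0.6 | 1.5% | 56 |

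A closed form agrees. The share of the variance of the log risk ratio removed is 2v / [(1−0.15)/0.15 + (1−0.225)/0.225] = 2v/9.111, where v = [(1+RR²)/2]² / [(1+RR)/2]⁴ − 1. For RR 0.6, v = 0.4624/0.4096 − 1 = 0.129. The share is then 2.8% and the SE is larger by 1.4%. The simulation (400 replicates) showed no detectable change in power.

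**5. Bias through missing data.** Assume one omitted binary covariate with 50% prevalence and an effect of 0.1 to 0.3 SD, no covariate-by-arm interaction, and missingness of 15% at one level and 25% at the other (20% overall).

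- *Same pattern in both arms:* the covariate mix among completers shifts equally, so the bias is 0.
- *Pattern in one arm only:* the higher-missing level makes up 0.75/(0.75+0.85) = 0.469 of completers instead of 0.5, a shift of 0.031. The bias is 0.031 × (0.1 to 0.3) = 0.003 to 0.009 SD.
- *Opposite patterns in the two arms:* the difference in mix is 0.0625. The bias is 0.006 to 0.019 SD.

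**The case against.** The strongest reply is that nothing has been dropped. SAP 15.0 refers to the Aim 1 approach, Aim 1 contains both variables, and the closing list is not said to be exhaustive. That reading is possible. But the list is the more specific text, and the Protocol repeats it. If the longer set was meant, the list is incomplete and needs the same edit.

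A second reply is that a shorter pre-specified list is legitimate, and that the plan calls the two variables predictive only of the primary outcome. This largely stands. SAP 13.0 lists multiple pain conditions and mood disorders as candidates within a class that extends to "any other variables thought to be associated with primary or secondary outcomes, moderate intervention (subgroups) or predict drop-out". That is general support only. It does not say that they predict any particular secondary outcome.

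A reader might infer four stronger things that the documents do not support:

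- **That secondary estimates will be biased.** Randomization protects complete-data comparisons, and step 5 gives no bias unless the link with missingness differs by arm. No such difference is documented. SAP 16.0 expects complex patients to do better with a live coach, but that concerns benefit, not survey response. SAP 11.0 also plans pattern-mixture imputation with inverse probability weights when 3-month missingness exceeds 15% or differs by group. This may reduce any bias, although the SAP does not name the weight predictors or say that the approach covers secondary outcomes.
- **That the 19-to-98-patient range applies to every outcome.** It is a linear-model figure. The subscale MCIDs are binary, so step 4 applies to them.
- **That nothing else informs the global impression of change items.** They have no baseline of their own, but baseline pain severity and all strata are in the model.
- **That the SAP and Protocol contradict each other.** They agree. The tension is within SAP 15.0 and between it and SAP 14.0.

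**Conclusion.** The point holds as a minor, nearly free improvement. The explicit list for the secondary outcomes other than MCID in pain severity, and for the exploratory outcomes, is shorter than the primary model's list, and no reason is given.

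The cost is a standard error about 0.5% to 2.6% larger for continuous outcomes and about 0.06% to 1.5% larger for binary ones, plus a narrower conditioning set for MAR. Illustrated bias runs from 0 to 0.019 SD. These sizes rest on assumed partial R², risk ratios and missingness patterns. If each outcome's own baseline value were also in its model, the precision gain from the two variables would be near the low end. The primary analysis and the sample size are unaffected.

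**What to change.** In SAP 15.0 (and so in 17.0) and Protocol 15.6, replace the covariate list with the SAP 14.0 set: baseline pain severity, sex, site, rural/medically underserved residency, multisite pain and co-occurring mental health condition. Say that the last two are the EHR-based variables defined in SAP 4.0, if that is what is meant. If the sponsor prefers the shorter list, SAP 15.0 should say so, give a reason, and stop implying that the Aim 1 covariates carry over.

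The cost is two extra model terms, negligible with about 1,863 evaluable participants. On the SAP 4.0 definitions, both variables are baseline EHR data already needed for the primary model, so no new collection is required.

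The text edit must be logged before unblinding, as SAP 2.0 requires. SAP 2.0 gives the SAP precedence over the Protocol's analysis plans and requires a protocol amendment only for changes to the primary endpoint or its analysis. The SAP edit can therefore govern, and Protocol 15.6 can be aligned through the IRB review that Protocol 19.2 requires for any amendment.
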